Alternative definitions of constipation that are CF specific will be created based on different frequencies of bowel movement and Bristol stool type evaluated individually or in combination. Spearman correlations of stool frequency with the PAC-SYM score and Bristol stool type with PAC-SYM scores will be examined. The different constipation definitions will be evaluated by comparing against the area under the curve of receiver operating characteristic curve (ROC curve) for PAC-SYM scores. The percentage of subjects reporting constipation based on self-assessment and the concordance to the protocol definition/alternate definitions will be made using Cohen's kappa coefficient.

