## 15.7 Sample Size

[figure not shown]
Sample size estimates for this study are based on two criteria:

- a. To assess feasibility and ensure representativeness of the enrolled CF subjects
- b. To estimate prevalence of GI symptoms (specifically constipation)

Period prevalence is defined as the proportion of subjects with symptom over an interval of time. Estimates of constipation prevalence in CF patients varies in the literature. A recent 2017 publication (7) showed the period prevalence of constipation over 3 months was 31% (32% adults; 30% children). Another 2010 publication (3) estimated prevalence of constipation in CF patients age  $\leq$  18 years in the Netherlands at 20% (annual assessment) using the ESPGHAN definition. Note that an epidemiologic review of constipation prevalence in the general population (non-CF) in North America ranged from 1.9% to 27.2% with most estimates from 12%-19% (19). Therefore, 10% will serve as the lower bound estimate of constipation prevalence. The sample size estimate for CF patients in the GALAXY study is based on a prevalence of constipation over a 1 month period in the 20% - 30% range (25% average).

Sample size estimates are based on 95% confidence intervals (C.I.) half-widths (i.e., width of one arm of the 95% CI) for proportions. While constipation is one symptom of interest, it is difficult to specify an exact prevalence estimate over a 1 month period utilizing the study specific definition of constipation. In addition, the occurrence of other GI symptoms is also of interest and will occur at varying rates. Therefore, the figure below shows what the sample size (y-axis) is for varying half-width sizes (x-axis) when prevalence estimates range between 10% to 50% (maximum). Approximately 400 subjects are needed to estimate a prevalence of constipation of 25% with a 95% C.I. half-width of 4.5% (95% C.I. = 20.5%, 29.5%) and assuming a 12% missing data rate.

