2.3 Definition of the Analysis Populations

Enrollment:

An enrolled participant was defined as a participant who had met all eligibility criteria, and fully completed (i.e. no question left unanswered) at least one of the ePRO questionnaires (PAC-SYM, PAGI-SYM, PAC-QOL, and disease-specific) at baseline.

Baseline:

Baseline refers to the enrollment visit of enrolled participants, at which informed consent was given, eligibility was met, and medical history was collected.

Follow-up weeks:

GALAXY Statistical Analysis Plan 12/16/2019 - CONFIDENTIAL

Follow-up occurred at week 1 (day 7, +1), week 2 (day 14, +1), and week 4, (day 28, +1). These were outside-of-clinic, i.e. participants are asked to complete the ePRO via their mobile devices. The questionnaires took approximately 10 minutes to complete. For participants \geq 2 years of age to $<$ 12 years of age, the parent/guardian completed the questionnaire. For participants \geq 12 years of age, the participant completed the questionnaire.

Protocol-defined constipation:

Per protocol, constipation is defined as $<$ 3 bowel movements in the past week and/or Bristol Stool type 1 or 2.

3. Overview of Planned Analyses

Unless otherwise noted, the endpoints of this study are mostly descriptive, with all continuous outcomes such as symptom severity and PRO scores evaluated using descriptive statistics such as mean, median, standard deviation, and 95% confidence intervals. Presence/absence of symptoms will be shown as percentages and corresponding 95% confidence intervals calculated using the Wilson method. Longitudinal models will be mixed-effect models with participant-specific random effect and compound symmetry covariance structure. Except where otherwise noted, all tests will be two-sided and statistical significance will be determined at the 0.05 level. No adjustment for multiple comparisons will be made.

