Descriptive statistics will be used to summarize the total and domain scores by protocol-defined constipation. Longitudinal summaries will be provided, using mixed-effect models with participant-specific random intercepts, as well as fixed effects for weekly protocol-defined constipation status, visit, and age group. The predictor of interest is the protocol-defined constipation status. The corresponding analyses are outlined in Appendix A, Section A.5.

Evaluation of alternative CF-specific definitions of constipation:

14. Examine alternative definitions of constipation that are CF specific based on correlation with PRO questionnaires and maximizing the area under the receiver operating characteristic (ROC) curve for PAC-SYM scores
15. Number (%) reporting constipation based on patient self-assessment. Examine concordance of self-reported constipation against protocol/alternate definitions using Cohen's kappa coefficient

The corresponding analyses are outlined in Appendix A, Section A.6.

3.4.3 Current management of GI symptoms:

16. Number (%) of all participants receiving treatment at baseline
17. Number (%) of all participants initiating treatment at baseline
18. Number (%) of all participants receiving treatment by medication class/type
19. Among participants with GI symptoms and constipation, number (%) receiving treatment
20. Change in distribution of GI symptoms and stool frequency/type by GI treatment at baseline
21. Mean PRO scores (also mean differences and 95% confidence interval) by GI treatment at baseline
22. Among participants receiving or initiating treatment for constipation, mean absolute change in PRO scores over time overall and by medication type/class

The corresponding analyses are outlined in Appendix A, Section A.7.

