		Protocol-Defined Constipation at Baseline		All Enrolled Participants (N=n)	Fully Completed at Least One ePRO at all Follow-up Weeks (N=n)	CF Registry (N=n)
		Yes (N=n)	No (N=n)			
Genotype, n (%)	F508 Heterozygous F508 Homozygous Other/Unknown					
Mutation Class, n (%)	I-III IV-V Unknown					
Sweat Chloride at Diagnosis (mEq/L)	Mean (SD)					
Weight (kg)	Mean (SD)					
Height (cm)	Mean (SD)					
Pancreatic Sufficiency[1], n (%)	Insufficient Sufficient Unknown					
Modulator Use, n (%)	None Ivacaftor Ivacaftor/Lumacaftor Ivacaftor/Tezacaftor Ivacaftor/Tezacaftor/Elexacaftor					

[1] Pancreatic Insufficient is defined as PERT use and/or fecal elastase or other diagnostic test at baseline.
Note on missing demographic data

Exhibit 5.2.2 Summary of Period-Prevalence of Constipation with Disease-Specific Questionnaire Fully Completed at all Weeks

This table summarizes the period-prevalence of protocol-defined constipation, as well as other definitions of constipation. Only participants who fully completed the disease-specific questionnaire at baseline and all follow-up weeks were considered. Period prevalence is defined as occurrence of the symptom at any time from baseline to week 4.

	Age <18 Years (N = n)	Age ≥18 Years (N = n)	All Participants (N = n)
Protocol-Defined Constipation ^[1] :	% (95% CI)		
Self-Described Constipation ^[2]			
Constipation			
Alternating Constipation and Diarrhea			
Alternative Definition:			
Definition 1			
...			
Definition d			

[1] Protocol-defined constipation is defined as less than 3 bowel movements and/or Bristol Stool type 1 or 2 in the past week

[2] Self-described constipation is based on the second question on the disease-specific questionnaire

Note: See Appendix B for discussion regarding alternative definitions of constipation.

Exhibit 5.2.3 Summary of Period-Prevalence of Constipation with Disease-Specific Questionnaire Fully Completed at least once

Similar table as above with consideration of participants who fully completed the disease-specific questionnaire at least once.

Exhibit 5.3.1 Summary of GI Symptoms from PAC-SYM, PAGI-SYM, and PAC-QOL

This table summarizes the GI symptoms based on prespecified questions from PAC-SYM, PAGI-SYM, and PAC-QOL questionnaires. All questions were based on patient's experience in the last week.

	Baseline	Week 1	Week 2	Week 4	Overall [1]
Symptom 1					
N [2]					
Absent, n (%)					
Mild, n (%)					
Moderate, n (%)					
Severe, n (%)					
Very Severe, n (%)					

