The following table shows the changes in GI symptoms from baseline at each follow-up week. This is a collapsed version with less details compared to the 5.4.x exhibits.

GI Symptom	Baseline Mean (95% CI)	Week 1					Week 2					Week 4				
		N [1]	Mean (95% CI)	Worsen – n (%)	No Change – n (%)	Improved – n (%)	N [1]	Mean (95% CI)	Worsen – n (%)	No Change – n (%)	Improved – n (%)	N [1]	Mean (95% CI)	Worsen – n (%)	No Change – n (%)	Improved – n (%)
Symptom 1	Mean (95% CI)	n	mean (CI)	n (%)	n (%)	n (%)	n	mean (CI)	n (%)	n (%)	n (%)	n	mean (CI)	n (%)	n (%)	n (%)
Symptom 2																
...																
Symptom s																

[1] N per each follow-up week is defined as the number of participants who had data at both baseline and the follow-up week.

Exhibit 5.5.1 Summary of PAC-SYM, PAGI-SYM, and PAC-QOL Total Score by Protocol-Defined Constipation

This figure summarizes the distribution of total scores for PAC-SYM, PAGI-SYM, and PAC-QOL by **weekly** protocol-defined constipation status

[figure not shown]
[figure not shown]

Exhibit 5.5.2 Summary of PAC-SYM, PAGI-SYM, and PAC-QOL Total Score by Self-Defined Constipation

Similar figure to Exhibit 5.5.1 but using self-defined constipation.

Exhibit 5.6.1 Model-based Summary of PAC-SYM, PAGI-SYM, and PAC-QOL Total and Domain Scores by Protocol-Defined Constipation

This figure provides model-based summaries of the total and domain scores, for all participants and by weekly protocol-defined constipation. The estimates are obtained from mixed-effect models with participant-specific random intercepts, as well as fixed effects for protocol-defined (weekly) constipation status, week, and age group. The predictor of interest is constipation status.

Exhibit 5.6.2 Model-based Summary of PAC-SYM, PAGI-SYM, and PAC-QOL Total and Domain Scores by Self-Defined Constipation

Similar figure to Exhibit 5.6.1 but using self-defined constipation.

A.6 Summary of Alternative CF-Specific Definitions of Constipation

Exhibit 6.1.x Summary of PAC-SYM total score by constipation status defined by [protocol or specific rules]

This figure (one figure per one definition of constipation) shows how the distribution of PAC-SYM total score looks with different definition for constipation, and an in-sample ROC curve constructed by using PAC-SYM total score in a longitudinal model as a classifier for the corresponding weekly constipation status.

[figure not shown]

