[1] Unknown status of constipation at each week is defined as either incomplete Disease-Specific Questionnaire or failure to answer question 2 on the Disease-Specific Questionnaire.

[2] To summarize all follow-up weeks, constipation status implies that a participant had at least one or more week where they met the self-defined definition of constipation.

Exhibit 6.4.x Model-Based Summary of Clearance of Constipation among Participants Who Had Constipation at Baseline Visit.

This exhibit reports statistical results for the clearance of constipation among participants who had constipation at baseline visit and had at least one follow-up Disease-Specific Questionnaire fully completed. Weekly clearance of constipation (1=yes, 0=no) is the outcome of interest in a generalized linear mixed model (GLMM) with either logit link (for odds ratio interpretation) or log link (for relative risk interpretation), participant-specific random effects, and adjustments for baseline constipation treatment, age group, sex, and week. In formula:

Weekly Clearance of Constipation (0/1) ~ Baseline Constipation Treatment + Age Group + Sex + Week + Participant-Specific Random Effect

Note: Constipation treatment at baseline was determined based on ATC coding of concomitant medications.

Exhibit 6.4.1 for Protocol-Defined Constipation

Exhibit 6.4.2 for Self-Defined Constipation

Exhibit 6.5.x Model-Based Summary of Emergence of Constipation among Participants Who Had No Constipation at Baseline Visit.

This exhibit reports statistical results for the emergence of constipation among participants who had no constipation at baseline visit and had at least one follow-up Disease-Specific Questionnaire fully completed. Weekly emergence of constipation (1=yes, 0=no) is the outcome of interest in a generalized linear mixed model (GLMM) with either logit link (for odds ratio interpretation) or log link (for relative risk interpretation), participant-specific random effects, and adjustments for baseline constipation treatment, age group, sex, and week. In formula:

Weekly Emergence of Constipation (0/1) ~ Baseline Constipation Treatment + Age Group + Sex + Week + Participant-Specific Random Effect

Note: Constipation treatment at baseline was determined based on ATC coding of concomitant medications.

Exhibit 6.5.1 for Protocol-Defined Constipation

Exhibit 6.5.2 for Self-Defined Constipation

A.7 Summary of Current Management of GI Symptoms

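### SAP Exhibit 6.1.x does not say whether participant effects enter the ROC score; if they do, the AUC can exceed 0.9 even when PAC-SYM carries no information about constipation.

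*SAP*

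**What the plan says.** The protocol (section 15.4) evaluates alternative constipation definitions by "comparing against the area under the curve of receiver operating characteristic curve (ROC curve) for PAC-SYM scores". It mentions no model. SAP section 3.4.2, item 14, keeps that target and makes it a criterion: "maximizing the area under the receiver operating characteristic (ROC) curve for PAC-SYM scores".

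The exhibit that delivers this is SAP Appendix A.6, Exhibit 6.1.x, with one figure per definition. Besides the distribution of PAC-SYM totals, each figure shows "an in-sample ROC curve constructed by using PAC-SYM total score in a longitudinal model as a classifier for the corresponding weekly constipation status".

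SAP section 3 states what a longitudinal model is: "Longitudinal models will be mixed-effect models with participant-specific random effect and compound symmetry covariance structure". For Exhibit 6.1.x the text gives no link, covariates or formula. Two exhibits in the same appendix do have one; Exhibit 6.4.x, for example, is written as "Weekly Clearance of Constipation (0/1) ~ Baseline Constipation Treatment + Age Group + Sex + Week + Participant-Specific Random Effect".

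**The concern.** A fitted mixed model offers at least two scores for each participant-week: the fixed part alone, or the fixed part plus the predicted participant effect. The plan does not choose, and each option has a consequence.

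- **Participant effect included.** The effect is estimated from the participant's own constipation answers, and the ROC then asks how well the score classifies those answers. The AUC mostly reflects how the definition clusters within people, not what PAC-SYM contributes.
- **Fixed part only, PAC-SYM the sole predictor.** Apart from sign, the score ranks weeks exactly as raw PAC-SYM does, so the model adds nothing.
- **Fixed part only, with week and age group added** as in the SAP's other models. The AUC no longer belongs to PAC-SYM alone.

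Only the first option does serious damage, but a literal reading permits it. It bears on the comparison the exhibit exists to make. The definitions in SAP Appendix B overlap by construction: two are components of the protocol definition, and the rule of fewer than 7 movements contains the rule of fewer than 3. Their prevalences will generally differ, and their week-to-week persistence may too. An AUC that responds to both can favour a definition for reasons unrelated to PAC-SYM.

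**Working it through.** **Inputs from the documents**

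- 400 participants, 25% one-month prevalence (range 20% to 30%), half-width 4.5%, 12% missing: protocol 15.7.
- Four assessments (baseline, weeks 1, 2 and 4): SAP 2.3. Prevalence counts all four: "Period prevalence is defined as occurrence of the symptom at any time from baseline to week 4" (Exhibit 5.2.2).
- PAC-SYM variance 0.52: protocol 15.7.

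**Assumed:** the random-intercept SD (0 to 3), the log-odds per PAC-SYM point, and the between/within split of the 0.52.

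**Step 1. The plan's own figure.** n = 1.96² × 0.25 × 0.75 / 0.045² = 355.7, so 356. Allowing for 12% missing, 356/0.88 = 405 (or 356 × 1.12 = 399), consistent with about 400. Evaluable: 400 × 0.88 = 352, with half-width 1.96 × √(0.1875/352) = 4.5%. The documents state no AUC to reproduce.

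**Step 2. The mechanism by hand.** Suppose PAC-SYM has no effect. Participant effects then rank people by how many of their four weeks were constipated. Take the case with no persistence at all: weekly prevalence p = 1 − 0.75^(1/4) = 6.9%. Compare a constipated week with a non-constipated week from another person. The counts are 1 + B and B′, both B and B′ being Binomial(3, p) with probabilities 0.806, 0.180, 0.013 and 0.0003 for 0 to 3.

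- P(B′ = B + 1) = 0.148
- P(B′ ≥ B + 2) = 0.011
- AUC = 1 − 0.011 − 0.148/2 = 0.915

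The constipated week counts itself, and that alone is enough to pass 0.9.

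**Step 3. The fitted model under the null.** 352 participants × 4 assessments; weekly status from a random-intercept logistic model calibrated to 25% period prevalence; PAC-SYM independent of status (variance 0.52, split 60/40 between/within); maximum-likelihood fit by Gauss-Hermite quadrature; 30 replicates per row. Latent ICC = SD²/(SD² + 3.29).

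| SD | ICC | Weekly prevalence | Mean AUC with participant effect | Runs above 0.9 | Fixed part only | Raw PAC-SYM |
|---|---|---|---|---|---|---|
| 0 | 0 | 6.9% | 0.676 | 23% | 0.520 | 0.496 |
| 0.5 | 0.07 | 7.1% | 0.741 | 33% | 0.525 | 0.488 |
| 1 | 0.23 | 7.7% | 0.919 | 93% | 0.528 | 0.495 |
| 1.5 | 0.41 | 8.8% | 0.939 | 100% | 0.525 | 0.498 |
| 2 | 0.55 | 10.0% | 0.954 | 100% | 0.524 | 0.499 |
| 3 | 0.73 | 12.4% | 0.971 | 100% | 0.520 | 0.488 |

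At SD 0 the single runs span 0.49 to 0.93. Where the estimated variance is practically zero the participant effects vanish; where it is positive, the Step 2 ranking takes over.

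At SD 1 and SD 2 the means are 0.935 and 0.960 for 20% period prevalence, 0.916 and 0.948 for 30%, and 0.878 and 0.926 for 50%.

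**Step 4. Covariates.** With week and age group added (15% weekly prevalence, 40% pediatric, 60 replicates per setting), the fixed-part null AUC is 0.55, or 0.57 to 0.60 if age group has a log-odds of 0.7.

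**Step 5. Ranking.** Definition A is more closely tied to PAC-SYM (log-odds 2 per point, SD 1). Definition B is less so but more persistent (log-odds 1, SD 2). PAC-SYM variance is split 0.40/0.12; 100 replicates.

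| Setting | Raw AUC, A v B | AUC with participant effect, A v B | Order reversed |
|---|---|---|---|
| Both at 15% weekly (period prevalence 38% and 34%) | 0.79 v 0.64 | 0.89 v 0.95 | 99% |
| Both at 25% period prevalence (weekly 8.8% and 10.1%) | 0.81 v 0.64 | 0.90 v 0.96 | 98% |

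With both definitions at SD 1, reversal falls to 52% when B is rarer (10% v 25% weekly) and to 13% when B is commoner (25% v 10%).

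**The case against.** - **The harmful reading is not stated.** The SAP keeps the target as the ROC for PAC-SYM scores and nowhere mentions participant-level prediction. An analyst could well use the fixed part only. This stands, and it is why the point is conditional.
- **The mock-up figure is missing from the copy reviewed.** It might have carried model detail. This also stands; the point rests on the text.
- **The SD is assumed, and the size depends on it.** True. At SDs of 0 to 0.5 the mean null AUC is 0.68 to 0.74, so passing 0.9 on average takes an SD of about 1 or more at the planned prevalence. A wholly uninformative PAC-SYM is a stress case, chosen to isolate the artefact.
- **The reversal example is constructed.** A has twice B's log-odds and half its SD, and the documents support neither value. It shows what can happen, not how likely it is. It does not depend on prevalences outside the planning range, since it persists with both definitions at 25%.
- **There are safeguards.** The word in-sample is disclosed, the same figure shows the PAC-SYM distributions, and Spearman correlation and kappa do not use this model. These would help a careful reader. However, in-sample normally signals mild optimism: 0.02 to 0.03 here for the fixed part, against about 0.42 or more from participant effects at an SD of 1 or above.

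**Conclusion.** The concern holds. As written, the plan allows the outcome into its own classifier, on the one criterion it says to maximise. If participant effects are used, an uninformative PAC-SYM yields a mean AUC of 0.92 to 0.97 at 25% period prevalence for random-intercept SDs of 1 to 3, against 0.52 to 0.53 from the fixed part. The order of two definitions can then reverse. These sizes rest on the assumed SD, log-odds and variance split.

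The consequence is confined to a secondary, descriptive comparison that also uses correlation and kappa and has no formal selection rule. This should be settled before the analysis is run, but it does not threaten the study's main results.

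**What to change.** In Exhibit 6.1.x, compute the AUC directly from the weekly PAC-SYM total against each definition, by visit and pooled over visits, with no participant effects in the score. Give confidence intervals, and paired differences in AUC between definitions, from a bootstrap that resamples whole participants so that repeated weeks stay together.

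If a longitudinal model is kept, write out its formula, as Exhibits 6.4.x and 6.5.x do, and state that the ROC score uses fixed effects only. If week or age group is in the model, say that the AUC is that of the combined score.

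The cost is one or two sentences in the SAP and a little programming for the bootstrap. No new data are needed. The reported AUCs may be lower.

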[1] 'All Enrolled Participants' are those who met study eligibility criteria and fully completed at least ePRO at baseline visit (Visit 1).

[2] Pancreatic Insufficient is defined as PERT use and/or fecal elastase or other diagnostic test at baseline.

Note on missing demographic data

A.3 Summary of ePRO Completion

Exhibit 3.1.x Completion of ePRO Questionnaires – [All or Subgroups Defined by Age here]

This table summarizes ePRO completion rate across baseline and follow-up weeks. “Fully completed” a questionnaire is defined as having responded to all questions with no missing responses.

Week	PAC-SYM	PAGI-SYM	PAC-QOL	Disease-Specific	Fully Completed at Least One ePRO	Fully Completed all ePROs
Baseline (N=n)	n (%)					
Week 1 (N=n)	n (%)			X		
Week 2 (N=n)	n (%)			X		
Week 4 (N=n)	n (%)					
All follow-up weeks	n (%)					

Note: PAC-QOL was only collected at Baseline and Week 4.

Exhibit 3.1.1 Completion of ePRO Questionnaires – All Participants

Exhibit 3.1.2 Completion of ePRO Questionnaires – Age <18 Years

Exhibit 3.1.3 Completion of ePRO Questionnaires – Age ≥18 Years

Exhibit 3.2.1 Missing Data for ePROs by Follow-up Week and Participant

This figure helps to visualize the number of not-fully-completed ePROs at each week by participant. Data for each study participant is represented by a row. The color indicates the number of not-fully-completed ePROs at each week. For example, at baseline, enrolled participants are defined as those with eligibility and fully completed at least one ePRO. Hence, for each participant at baseline, there can only be zero, one, two, or three ePROs missing. Similarly, since PAC-QOL is not collected at Weeks 1 and 2, there can only be zero, one, two, or three ePROs missing.

[figure not shown]

Exhibit 3.2.2 Missing Data for ePROs by Participant with Age < 18
Exhibit 3.2.3 Missing Data for ePROs by Participant with Age ≥ 18

Exhibit 3.3 Completion of ePROs by Site

This table summarizes ePRO completion by site

Site	Number of Participants	Fully Completed at Least One ePRO at All Follow-Up Weeks (Weeks 1,2 & 4)	Fully Completed all ePROs at All Follow-Up Weeks (Weeks 1, 2 & 4)
Site 1			
Site 2			
...			
Site s			
Overall			

A.4 Summary of PAC-SYM, PAGI-SYM, and PAC-QOL Scores

Exhibit 4.1 Distributions of Total Scores for PAC-SYM, PAGI-SYM, and PAC-QOL for All Participants

This figure summarizes the total scores for PAC-SYM, PAGI-SYM, and PAC-QOL at each week and overall, for all participants.

[figure not shown]

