Stool Symptoms (NN=nn)									
PAGI-SYM Total Score (NN=nn)									
Nausea/Vomiting (NN=nn)									
Post-Prandial Fullness/Early Satiety (NN=nn)									
Bloating (NN=nn)									
Upper Abdominal Pain (NN=nn)									
Lower Abdominal Pain (NN=nn)									
Heartburn/Regurgitation (NN=nn)									
PAC-QOL Total Score (NN=nn)									
Physical Discomfort (NN=nn)									
Psychosocial Discomfort (NN=nn)									
Worries and Concerns (NN=nn)									
Satisfaction (NN=nn)									

A.5 Summary of Prevalence and Variability of GI Symptoms

Exhibit 5.1.1 Summary of Disease-Specific Questionnaire – All Participants

This table summarizes the GI disease-specific questionnaire for all participants. All questions were based on patient's experience in the last week.

		Baseline (N=n)	Week 1 (N=n)	Week 2 (N=n)	Week 4 (N=n)
Bowel Movements	<3 Bowel Movements ≥3 Bowel Movements		n (%)		
Self-Described Bowel Pattern:	Normal Constipated Diarrhea Alternating Constipation and Diarrhea				
Bristol Stool Scale ^[1] :	1 (Hard Lumps) – 2 3 – 5 6 – 7 (Watery) Missing				
Leakage of Stool:	Yes				
Protocol-Defined Constipation ^[2]:	Yes				

[1] Question for Bristol Stool Scale: describe what your stool looked like on most days in the last week when you had a bowel movement?

[2] Protocol-defined constipation is defined as less than 3 bowel movements and/or Bristol Stool type 1 or 2 in the past week

Exhibit 5.1.2 Summary of Disease-Specific Questionnaire – Age < 18

Exhibit 5.1.3 Summary of Disease-Specific Questionnaire – Age ≥ 18

Exhibit 5.2.1 Demographics and Baseline Characteristics by Protocol-Defined Constipation at Baseline.

This table summarizes demographics and baseline characteristics, stratified by protocol-defined constipation at Baseline Visit.

	Protocol-Defined Constipation at Baseline		All Enrolled Participants (N=n)	Fully Completed at Least One ePRO at all Follow-up Weeks (N=n)	CF Registry (N=n)
	Yes (N=n)	No (N=n)			
Sex at Birth, n (%)	Female				
	Male				
Age Distribution, n (%)	<6 years				
	≥6 – 12 years				
	≥12 – 18 years				
	≥18 – 24 years				
	≥24 – 30 years				
	≥30 years				
	Mean (SD)				
	Median				
	Min, Max				
Race, n (%)	White				
	American Indian or Alaska Native				
	Black or African American				
	More than One Race				
	Unknown or Not Reported				
Ethnicity, n (%)	Hispanic or Latino				
	Not Hispanic or Latino				

CF Therapeutics Development Network Coordinating Center
GALAXY-OB-18

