Exhibit 6.2.x Evaluation of Concordance between Self-Defined Constipation and Constipation Defined by [Protocol or Specific Rules]

This table shows the concordance between self-defined constipation and the definition of interest

	Self-Defined Constipation		Cohen's Kappa
	Yes	No	
Constipation Definition of Interest:	Baseline (N=n)	Yes No	n (%)
	Week 1 (N=n)	Yes No	
	Week 2 (N=n)	Yes No	
	Week 4 (N=n)	Yes No	
	Overall (NN=nn)	Yes No	
			x

Exhibit 6.3.1 Evaluation of Protocol-Defined Constipation at Baseline and Constipation Treatment.

This table shows the relationship between constipation at baseline and constipation treatment. Constipation is defined per protocol.

		Constipation at Baseline (N=n)		No Constipation at Baseline (N=n)		All Participants at Baseline (N=n)	
		On Treatment (N=n)	Not on Treatment (N=n)	On Treatment (N=n)	Not on Treatment (N=n)	On Treatment (N=n)	Not on Treatment (N=n)
Week 1	Constipation	n (%)	n (%)				
	No Constipation	n (%)	n (%)				
	Unknown [1]	n (%)	n (%)				
Week 2	Constipation						
	No Constipation						
	Unknown [1]						
Week 4	Constipation						
	No Constipation						
	Unknown [1]						
All Follow-up Weeks [2]	Constipation						
	No Constipation						
	Unknown						

[1] Unknown status of constipation at each week is defined as incomplete Disease-Specific Questionnaire

[2] To summarize all follow-up weeks, constipation status implies that a participant had at least one or more week where they met the protocol definition of constipation.

Exhibit 6.3.2 Evaluation of Self-Defined Constipation at Baseline and Constipation Treatment.

This table shows the relationship between self-defined constipation at baseline and constipation treatment. Constipation is defined as choosing "Constipated" or "Alternating constipation and diarrhea" as answer for question 2 ("How would you describe your bowel pattern in the last week? (Select one)") on the Disease-Specific Questionnaire.

		Constipation at Baseline (N=n)		No Constipation at Baseline (N=n)		All Participants (N=n)	
		On Treatment (N=n)	Not on Treatment (N=n)	On Treatment (N=n)	Not on Treatment (N=n)	On Treatment (N=n)	Not on Treatment (N=n)
Week 1	Constipation	n (%)	n (%)				
	No Constipation	n (%)	n (%)				
	Unknown [1]	n (%)	n (%)				
Week 2	Constipation						
	No Constipation						
	Unknown [1]						
Week 4	Constipation						
	No Constipation						
	Unknown [1]						
All Follow-up Weeks [2]	Constipation						
	No Constipation						
	Unknown						

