Appendix B: Definitions of Constipation

Protocol-defined constipation: <3 bowel movements AND/OR BSS type 1 or 2.

Self-described constipation (based on disease-specific questionnaire)

- Definition 1: Answered “Constipated” for question 2 on disease-specific questionnaire
- Definition 2: Answered “Constipated” or “Alternating constipation and diarrhea” for question 2 on disease-specific questionnaire

Other alternative definitions to be considered:

- Proposed definition 1: <3 bowel movements (rationale: subset of the protocol definition)
- Proposed definition 2: BSS type 1 or 2 (rationale: subset of the protocol definition)
- Proposed definition 3: <7 bowel movements (rationale: the disease-specific questionnaire is a weekly survey, and having <7 bowel movements is equivalent to not having at least 1 bowel movement per day on average)

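### SAP Exhibits 6.3.1–6.3.2 and the period-prevalence tables tie constipation status to a complete disease-specific form, so a week that already meets the and/or definition can be lost to a blank item

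*SAP*

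**What the plan says.** SAP Appendix B gives the definition: "Protocol-defined constipation: <3 bowel movements AND/OR BSS type 1 or 2". SAP 2.3, the footnotes to Exhibits 5.1.1 and 5.2.2, and protocol 15.4 agree. Either component is enough, and none of these places adds a completeness condition.

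The weekly rows of Exhibit 6.3.1 carry a different rule: "Unknown status of constipation at each week is defined as incomplete Disease-Specific Questionnaire". For self-defined constipation, which rests on question 2, the footnote to Exhibit 6.3.2 reads: "Unknown status of constipation at each week is defined as either incomplete Disease-Specific Questionnaire or failure to answer question 2".

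Incomplete is not defined. Its apparent opposite is. SAP 2.3 glosses completion as "fully completed (i.e. no question left unanswered"), and Exhibit 3.1 says that a fully completed questionnaire "is defined as having responded to all questions with no missing responses".

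That defined term also selects participants elsewhere. Exhibit 5.2.2 takes only those with a fully completed disease-specific questionnaire at baseline and every follow-up week. Exhibit 5.2.3 asks for at least one such form. Exhibits 6.4.x and 6.5.x ask for at least one at follow-up.

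Exhibit 5.1.1 shows what the form holds: stool count, self-described bowel pattern, Bristol type and leakage. The Bristol question asks the participant to "describe what your stool looked like on most days in the last week when you had a bowel movement". Its response rows are types 1–2, 3–5, 6–7 and Missing. No other item in that table has a Missing row, and none of the Bristol rows stands for no bowel movement.

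**The concern.** Under an and/or rule, one observed positive component fixes the answer. Requiring the whole form discards that information. It does so even when the blank is in bowel pattern or leakage, which play no part in the protocol definition.

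The blanks need not be random. Someone with no bowel movement in the week has nothing to rate on the Bristol item, and that week is constipated by definition. If such blanks occur, they fall on the positive side of the outcome and push constipation estimates down. One endpoint exposed is the period prevalence, on which protocol 15.7 bases the sample size.

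**Working it through.** **1. The rules side by side.** The strict column reads incomplete as any item blank. BM is the number of bowel movements in the week.

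| Items reported in the week | And/or definition | Exhibit 6.3.1, strict reading | Item-level rule |
|---|---|---|---|
| BM <3, all items answered | met | Constipation | Yes |
| BM <3, Bristol blank | met | Unknown | Yes |
| BM <3, leakage or pattern blank | met | Unknown | Yes |
| BM blank, Bristol 1–2 | met | Unknown | Yes |
| BM ≥3, Bristol 3–7, leakage or pattern blank | not met | Unknown | No |
| BM ≥3, Bristol blank | undetermined | Unknown | Unknown |

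Rows 2 to 5 are settled by the definition but not by the footnote. For self-defined status, a participant who answered question 2 and left another item blank is in the same position.

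**2. The plan's own figure.** Protocol 15.7 gives p = 0.25, half-width h = 0.045, 12% missing and about 400 subjects.

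- n = 1.96² × 0.25 × 0.75 / 0.045² = 355.7, so 356 evaluable; 356/0.88 = 404.5, so 405.
- With 400 × 0.88 = 352 evaluable, the half-width is 1.96 × √(0.25 × 0.75/352) = 4.52 points.

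The figure reproduces and is not in dispute. It supplies the base for the illustration: 352 × 0.25 = 88 participants with constipation and 264 without.

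**3. Illustration for Exhibit 5.2.2, at participant level.** The documents give no rate of blank items, so both inputs are assumed. Let f be the share of constipated participants, and g the share of the others, excluded because of a blank item. The table then reads

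88(1−f) / [88(1−f) + 264(1−g)].

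| f | g = 0 | g = 2% |
|---|---|---|
| 2% | 24.6% | 25.0% |
| 5% | 24.1% | 24.4% |
| 10% | 23.1% | 23.4% |
| 20% | 21.1% | 21.4% |
| 30% | 18.9% | 19.2% |

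For example, f = 10% and g = 0 gives 79.2/(79.2 + 264) = 23.1%. With f = g there is no bias: only a difference in blank rates matters. With g = 0, the shortfall equals 4.5 points when 0.25(1−f)/(1−0.25f) = 0.205, that is f = 0.045/0.19875, about 23%.

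**4. From weekly blanks to f.** Exhibit 5.2.2 needs four complete forms. If blanks occur only in constipated weeks, at rate b and independently, then f is b for a participant constipated in one week and 1 − (1−b)⁴ for one constipated in all four. For b = 1%, 2%, 5% and 10% the latter is 3.9%, 7.8%, 18.5% and 34.4%. A given weekly rate therefore matters more for persistent constipation.

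**The case against.** **The strict reading is inferred.** The footnotes say incomplete, which is not the defined term. In Exhibit 6.3.2 a failure to answer question 2 is listed as a separate ground, which would be redundant if any blank made the form incomplete. Incomplete may mean only that the form was not returned. This stands for the two footnotes. It does not reach Exhibits 5.2.2, 5.2.3, 6.4.x and 6.5.x, which use the defined term.

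**The Unknown rule is local.** It is stated for the weekly rows of two descriptive tables, with Unknown shown as its own row, so the loss there would be visible. Exhibits 5.1.1, 6.1, 6.2 and 7.2 state no such rule. A participant can also count in the all-weeks row through another week. All of this stands. It also means that one week could be classified differently in different exhibits.

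**The clearance model.** A reader might infer that uncleared weeks are dropped, so that clearance looks better than it was. The text does not say so. The condition governs a participant's entry; whether that participant's partly completed weeks contribute is not stated.

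**The size.** A reader might set an assumed weekly-rate error, such as 25% reading 21.4%, against the planned 4.5-point half-width. That half-width belongs to period prevalence, an any-occurrence measure over a month, so the comparison is not valid for a single-week rate. Nor can a blank Bristol item affect weeks that qualify through Bristol 1–2, because the item was answered in those weeks.

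**Blanks may be impossible.** The questionnaire is not reproduced. Forced entry, skip logic or a no-movement option cannot be excluded. The Missing row in Exhibit 5.1.1 suggests that blanks were foreseen, but it could also reflect forms not returned.

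**Conclusion.** The point holds in a limited form. Selecting on a fully completed form conflicts with the SAP's and/or definition in the period-prevalence tables, because a participant whose answers already establish constipation can be excluded for a blank in an irrelevant or inapplicable item. The same condition governs entry to the clearance and emergence models. In Exhibits 6.3.1 and 6.3.2 the conflict depends on incomplete meaning any item blank, which the SAP should settle either way.

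The likely direction is downward, on the assumption that blanks are more common in constipated weeks. The size cannot be computed from the documents. The assumed range above runs from no bias (equal blank rates) to about 6 points (30% of constipated participants lost and none of the others). It is nil if the app prevents blanks.

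This is a should-fix. The primary endpoint, completion of outside-the-clinic assessments, does not use constipation status and is unaffected.

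**What to change.** Define one weekly status variable from the items that each definition uses:

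- **Protocol-defined:** Yes if a stool count below 3 or Bristol 1–2 is observed, even if the other is blank; No only if both are observed and neither is met; Unknown otherwise. Zero bowel movements with a blank Bristol item is Yes.
- **Self-defined:** question 2 alone; Unknown only if it is blank.

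Use this status in place of full completion for Exhibits 5.2.2–5.2.3 and 6.3–6.5, and wherever else weekly constipation is reported. Say which weeks enter the models in 6.4.x and 6.5.x. Replace or define incomplete in the two footnotes. State how the app handles the Bristol item after zero movements. Keep full completion for the feasibility tables.

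The item-level rule is asymmetric: one item can establish Yes, but No needs both. Report the number of Unknown weeks, with bounds counting them all as No and then all as Yes.

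The cost is SAP wording and one derived variable per definition. No new data are needed. Missed assessments are a separate matter and are not changed by this.
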